6.4.3.7 Duration of objective response

The duration of objective response will be determined for patients who have a best overall response of CR or PR. Duration of objective response is defined as the time from first date of overall response of CR or PR until date of PD, or death due to any cause, whichever occurs first. If a patient did not die or progress then the date of the last radiological assessment will be used in the calculation.

Duration of objective response will be assessed separately by investigator assessment by RECIST 1.1 and by blinded central image review by mRECIST.

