PFS rates will be derived from the Kaplan-Meier estimates for each treatment group; 3, 6, 9, and 12-month TTP rates will be presented, together with 95% CIs. Quartiles will be presented and 95% CIs will be calculated on the quartiles for each treatment group. A log-rank (two-sided) test will be used to compare TTP between the two treatment groups at a 0.05 significance level. The HR and corresponding 95% CI will be computed from a Cox proportional hazards model. Plots of the Kaplan-Meier curves will be provided for each treatment group.

TPP, PFS, ORR and DCR, according to mRECIST criteria by blinded central image review, will be analyzed in the same way as the corresponding analysis of investigator assessed data described above.

Duration of objective response and duration of disease control by both blinded central image review and investigator assessment will be summarized by descriptive statistics (n, mean, SD, median, min, and max) by treatment group. Also, Kaplan-Meier analyses of duration of objective response and duration of disease control will be conducted.

Duration of response (months) = (Date of PD or death in absence of PD/Censor – Date of first overall response of CR or PR +1) /30.4375.

Duration of disease control rate (months) = (Date of PD or death in absence of PD/Censor – Date of first overall response of CR, PR or SD +1) /30.4375.

The censoring for duration of response and duration of disease control will be performed as follows:

- 1) If a patient received a subsequent HCC therapy before PD or death, or in the absence of PD or death, the duration of response and duration of disease control will be censored at the last valid post baseline radiological tumor assessment on or before the start date of the subsequent HCC therapy.
- 2) If a patient is known not to have died or have PD and did not receive subsequent HCC therapy, the duration of response and duration of disease control will be censored at the last valid post baseline radiological tumor assessment date.

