- 3) If a patient had PD or died immediately after two or more missed visits (Note: a response of NE for a visit is not considered as a missed visit), the duration of response and duration of disease control will be censored at the time of the last valid post baseline radiological tumor assessment date that occurred before the missed visits. Given the scheduled visit scheme of tumor assessments (i.e. every 8 weeks), the definition of 2 missed visits will equate to 16 weeks since the previous tumor assessment.

DoR by both blinded central image review and investigator assessment will be summarized by descriptive statistics (number of patients, mean, standard deviation, median, minimum, and maximum) by treatment group. The number and percentage of patients achieving DoR with >10% tumor replacement by blinded central review and >20% tumor replacement by blinded central review will be summarized by treatment group. A 2-sample t-test will be performed to compare the mean DoR between treatment groups, and the corresponding 95% CI for the mean difference between the two treatment groups will be calculated.

PTTS by both blinded central image review and investigator assessment will be summarized by number and percentage of patients by treatment group at Week 8, 16, and 24. The 95% CIs for the PTTS rate for each of the treatment groups will be computed according to Wilson approach⁷. The PTTS rates will be compared between treatment groups using the continuity adjusted Wald test, and the corresponding 95% CI for the difference in PTTS rates between the two treatment groups will be calculated.

The percentage and absolute change from baseline in the sum of the longest diameters of target lesions on or before the start date of subsequent HCC therapy will be summarized separately at Week 8, 16, and 24 analysis visits (as defined in Table 3). A waterfall plot of the best percentage change in the sum of longest diameters for the best overall response will be presented.

The tumor marker for HCC (AFP) will be summarized with descriptive statistics (number of patients, mean, standard deviation, median, minimum, and maximum) for each time-point and change from baseline by treatment group. The number and percentage of patients achieving an AFP response, defined in Section 6.4.3.11, will also be summarized and compared between treatment groups using the continuity adjusted Wald test.

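### The plain mean, SD and median planned for duration of response and duration of disease control count censored times as completed durations; the Kaplan-Meier estimate planned beside them should be named as the reported one.

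*SAP*

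**What the plan says.** SAP 8.6.6 gives duration of objective response and duration of disease control two summaries. The first is descriptive: "Duration of objective response and duration of disease control by both blinded central image review and investigator assessment will be summarized by descriptive statistics". It lists the number of patients, mean, SD, median, minimum and maximum by arm. The next sentence adds the second: "Also, Kaplan-Meier analyses of duration of objective response and duration of disease control will be conducted".

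Both duration formulas in 8.6.6 take as their end point the "Date of PD or death in absence of PD/Censor", so a censor date stands in for the event date when no event is counted. Three rules create censored values:

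1. Subsequent HCC therapy. The rule opens "If a patient received a subsequent HCC therapy before PD or death, or in the absence of PD or death" and censors at the last valid scan on or before the start of that therapy.
2. No event and no new therapy. The rule opens "If a patient is known not to have died or have PD and did not receive subsequent HCC therapy, the duration of response" and censors at the last valid post-baseline scan.
3. PD or death straight after two or more missed visits: "the duration of response and duration of disease control will be censored at the time of the last valid post baseline radiological tumor assessment date", meaning the last one before the gap.

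SAP 6.4.3.7, for duration of objective response only, says: "If a patient did not die or progress then the date of the last radiological assessment will be used in the calculation".

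Section 8.6.6 does not say which summary is the headline one. For PFS it specifies Kaplan-Meier rates and quartiles with 95% CIs; for these two durations it specifies neither.

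**The concern.** Both endpoints are defined as time to PD or death. A plain mean, SD or median of values that end at either an event or a censor date describes something else: time to PD, death, new therapy, a gap in scanning or the last scan, whichever the rules select. Such a mean is too low as a description of durability, and ongoing responses are among those cut short.

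The report would also carry two medians by arm for each endpoint, possibly different, with nothing to tell the reader which to use. If the censored share differs between arms, the plain figures can differ between arms even where true durability is the same. What is at stake is a pair of descriptive tables, not a trial conclusion.

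**Working it through.** **No plan figure to reproduce.** The documents state no duration, number of responders or censored share for either endpoint. What can be checked is the direction of the error and how its size depends on assumptions.

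**Direction.** Let T be the true duration, C the censoring time and X = min(T, C) the value in the table. X never exceeds T, and X is below T for every censored patient. So mean(X) < mean(T) as soon as anyone is censored. The median of X falls only if enough censoring happens before the true median.

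**Exponential case.** If T is exponential with rate λ and C is independent with survival function G, then

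- E[X] = ∫ exp(-λt) G(t) dt
- P(event) = ∫ λ exp(-λt) G(t) dt = λ E[X]
- hence E[X] = E[T] × P(event) = E[T] × (1 - censored share).

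The plain mean is then short by exactly the censored share. If C is exponential too, X is exponential and its median is short by the same share. Illustration with an assumed true mean of 8.0 months (median 8.0 × ln 2 = 5.5): at 30% censored the plain mean is 8.0 × 0.70 = 5.6 and the plain median 5.5 × 0.70 = 3.9 months.

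**Other distributions.** Simulation with 400,000 durations per scenario, independent censoring, and 30% censored by assumption:

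| Durations | Censoring | Mean short by | Plain median short by | Kaplan-Meier median short by |
|---|---|---|---|---|
| Exponential | Exponential | 30.0% | 30.0% | 0.0% |
| Exponential | Uniform from 0 | 29.9% | 25.4% | -0.1% |
| Exponential | Fixed cut-off | 29.8% | 0.0% | 0.0% |
| Exponential | Late uniform | 29.9% | 0.0% | 0.0% |
| Weibull, shape 0.7 | Exponential | 42.3% | 32.3% | 0.2% |
| Weibull, shape 0.7 | Uniform from 0 | 43.7% | 26.2% | -0.2% |
| Weibull, shape 1.5 | Exponential | 22.7% | 25.7% | -0.1% |
| Weibull, shape 1.5 | Uniform from 0 | 21.9% | 22.8% | 0.1% |

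At 10% censored the mean is 7-16% short and the plain median 0-10%. At 50% (fixed cut-off not run) the mean is 37-66% short and the plain median 23-55%. The Kaplan-Meier median stays within 0.2% of the truth throughout.

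**Which rules are likely to bite.** Rule 2 may apply to few patients: death is an event, and SAP 7.4 reports 406 deaths, with everyone still in follow-up observed for over 40 months. Rules 1 and 3 are not limited in that way. Rule 3 discards a known event. With two missed visits set at 16 weeks, such a patient enters the plain table at least 112/30.4375 = 3.7 months shorter than the recorded event date would give. Rule 1 is not symmetric: under SAP Appendix 4, TheraSphere counts as subsequent therapy for a control patient, while treatment or re-treatment in the TheraSphere arm does not. That is a route to unequal censoring, but the documents give no numbers for it.

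**The case against.** The main defence is that the proper analysis is already planned. The Kaplan-Meier sentence follows directly, the censoring rules serve it, and SAP Appendix 2 states that patients without an event are censored in PROC LIFETEST. This stands: the error is confined to the plain statistics, and a reader who infers that all reported durations will be too short goes further than the text allows.

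Other inferences also fail on the documents:

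- **That the shortfall equals the censored share.** This holds for the mean only with exponential durations, and for the median only if censoring is exponential as well. The table shows how far it can miss.
- **That a false advantage for one arm will appear.** It needs unequal censoring. Appendix 4 makes that possible, but nothing in the documents gives its size or net direction.
- **That a test will rest on the biased means.** The two-sample t-test in 8.6.6 is for DoR, which SAP 6.4.3.9 defines as depth of response. No between-arm test is specified for either duration. Both sit under Additional Efficacy Variables (6.4.3), outside the secondary list in 6.4.2 and the hierarchy in 8.6.2.
- **That 6.4.3.7 treats the last scan as the end of the response.** It only names the date; rule 2 in 8.6.6 says the patient is censored there. It is also silent on disease control.

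Nor is Kaplan-Meier beyond question. The near-zero error above was found under independent censoring. Censoring at new therapy or after missed visits may be related to prognosis, and then Kaplan-Meier can be biased too. It is still the right summary for censored data; the plain mean is not.

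**Conclusion.** The point holds as a minor one about reporting. As written, the plain mean and SD, and possibly the plain median, do not estimate the durations that the SAP defines. The direction for the mean is certain once anyone is censored. The size cannot be stated for this trial: the 22-44% (mean) and 0-32% (median) ranges rest on an assumed 30% censored, the duration shapes tried and independent censoring. The primary analysis, the secondary endpoints, alpha and the sample size are untouched.

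**What to change.** In SAP 8.6.6, for both durations and both readers (investigator and central review):

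- Name the Kaplan-Meier median and quartiles with 95% CIs as the reported estimate, as the section already does for PFS quartiles.
- Show the numbers of patients, events and censored by arm, preferably with censoring split by rule so that any imbalance is visible.
- Delete the plain mean, SD and median, or keep them with a label saying that they include censored values. The n, minimum and maximum can stay under the same label.

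Optionally, reword 6.4.3.7 to say that the patient is censored at the last scan date, in line with rule 2 in 8.6.6.

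The cost is a sentence or two of text and a table label. The Kaplan-Meier analysis is already planned, and no new data are needed.

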8.7 Analysis of Safety

All safety analyses will be performed on the Safety Population.

8.7.1 Extent of Exposure to Study Treatment

Analyses of the extent of exposure to study treatment will be performed on the mITT, PP and Safety populations.

8.7.1.1 Extent of Exposure to TheraSphere

The extent of patient exposure to TheraSphere as defined in Section 6.5.1.1 will be summarized using descriptive statistics (as appropriate, including number of patients, mean, median, standard deviation, minimum, and maximum, or counts and percentages).

8.7.1.2 Sorafenib

The extent of patient exposure to sorafenib as defined in Section 6.5.1.2 will be summarized by treatment group using descriptive statistics (as appropriate, including

number of patients, mean, median, standard deviation, minimum, and maximum, or counts and percentages).

The cumulative dose of sorafenib (g) prior to progression according to RECIST 1.1 by investigator assessment will be the sum of all administered doses prior to progression date per patient.

Duration of sorafenib in weeks prior to progression according to RECIST 1.1 by investigator assessment will be calculated as:

- Duration of Treatment (weeks) prior to progression by investigator assessment = sum of all sorafenib administration periods (stop date – start date) for sorafenib started prior to progression date /7
- Dose intensity of sorafenib (mg/day) prior to progression by investigator assessment per patient will be calculated as:
- Dose Intensity (mg/day) prior to progression by investigator assessment = Cumulative dose of sorafenib (mg) started prior to progression / (Duration of treatment (weeks) prior to progression *7)
- Relative dose intensity of sorafenib (%) prior to progression by investigator assessment will be the dose intensity (mg/day) prior to progression divided by the one-day equivalent dose ($2 * 400 \text{ mg} = 800 \text{ mg/day}$) *100.

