6.5.1.2 Extent of Exposure to Sorafenib

Sorafenib exposure prior to progression (i.e. prior to date of progression) as assessed by investigator according to RECIST 1.1, will be presented as described below by treatment group.

- Number of patients who received sorafenib during the study
- Number of patients who received sorafenib prior to progression
- Reasons for not receiving sorafenib prior to progression
- Time to the start of sorafenib (days) prior to progression, defined as (start date of first sorafenib administration prior to progression - randomization date + 1)
 - This summary will also be produced separately for patients with unilobar and bilobar disease at baseline (Note that unilobar or bilobar disease is

from the stratification factor on the Randomization eCRF page, with any incorrect values at randomization replaced with the corrected value from the eCRF, or values from eCRF for patients enrolled after the changes in stratification factor)

- Cumulative dose (g) of sorafenib prior to progression
- Dose intensity (mg/day) of sorafenib prior to progression
- Relative dose intensity (%) of sorafenib prior to progression
- Duration of treatment (weeks) of sorafenib prior to progression
- Reason for Dose Delays and Changes for sorafenib prior to progression

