8.7.1.3 Extent of Study Exposure and Follow-up

The duration of study will be summarized by treatment group using descriptive statistics (number of patients, mean, median, standard deviation, minimum, maximum).

Duration on study (months) = (earlier of study exit date and death date – randomization date + 1) / 30.4375

In addition, an alternative method for determining duration of follow-up will be performed using the reverse Kaplan-Meier method for the mITT population. The censored values for OS will be reversed so that 1's will be 0's and 0's will be 1's. The median follow-up time will be derived from the Kaplan-Meier method using the OS values of overall survival and the reversed censoring values.

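### Sorafenib duration in SAP 8.7.1.2 is stop minus start without the added day used elsewhere, the cumulative dose has two cut-offs, and drug holidays do not lower the reported intensity

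*SAP*

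**What the plan says.** SAP 8.7.1.2 defines four linked quantities, all before investigator-assessed progression.

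- Cumulative dose is "the sum of all administered doses prior to progression date per patient".
- Duration in weeks is the "sum of all sorafenib administration periods (stop date – start date"), taken over sorafenib that began before the progression date and divided by 7.
- Dose intensity is "Cumulative dose of sorafenib (mg) started prior to progression / (Duration of treatment (weeks) prior to progression *7").
- Relative dose intensity is the dose intensity "divided by the one-day equivalent dose" of 800 mg/day, times 100.

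The SAP's other intervals of this kind are inclusive. Time to the start of sorafenib in SAP 6.5.1.2 is "start date of first sorafenib administration prior to progression - randomization date + 1". Duration on study in SAP 8.7.1.3 is the "earlier of study exit date and death date – randomization date + 1", converted to months. The times to first angiogram and first TheraSphere (SAP 6.5.1.1) and time to progression (SAP 8.6.2.1) also add one day.

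The SAP does not define the stop date, the day count behind the cumulative dose, or the handling of a record whose start and stop dates coincide. It lists no intensity measure that includes time off drug. The protocol permits drug holidays (Synopsis, Control Group), says that toxicity often makes them necessary (Section 5.3), and requires them to be recorded (Section 9.2.18) without describing the record layout.

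**The concern.** A course on days 1 to 14 has 14 dosing days, but subtracting the dates gives 13. If doses are counted on all 14 days and time on only 13, the ratio exceeds its natural ceiling. The loss recurs with each separate period, so an interrupted course is inflated more than an unbroken one of the same number of dosed days.

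Two further features affect what the table means. The stand-alone cumulative dose stops at progression, while the duration takes in whole periods that began before it. And days between periods never enter the denominator, so a patient who was off drug for a third of the course looks fully dosed.

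At stake is how well the exposure tables describe sorafenib delivery by arm. The SAP does not say what relative dose intensity is for, but a reader will naturally use it to judge whether sorafenib was delivered as well after TheraSphere as without it. Some interruptions arise only with TheraSphere: Protocol 9.2.15.1.3 describes sorafenib started first, stopped at least 7 days before TheraSphere and resumed at least 2 weeks after. An on-drug measure cannot show these.

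**Working it through.** **Inputs.** The reference dose is 2 × 400 = 800 mg/day, which reproduces the SAP's figure. The SAP states no duration or intensity result to reproduce. The patients below are illustrative, with start and stop both taken as full-dose days unless noted.

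**Formula as written.** Relative dose intensity (RDI) = 100 × cumulative mg / Σ(stop − start) / 800. For D dosed days at 800 mg in k separate periods this reduces to 100 × D / (D − k).

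**Day count, one period (k = 1).**

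| Dosed days | Calculation | RDI |
|---|---|---|
| 1 | 1 / 0 | undefined |
| 14 | 14 / 13 | 107.7% |
| 56 | 56 / 55 | 101.8% |
| 168 | 168 / 167 | 100.6% |

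The same 168 days split into 6 separate periods give 168 / 162 = 103.7%. With one day added per period, every row above becomes 100%, including the one-day course.

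**Progression cut.** Take full dose on days 1 to 84 in one period, with progression on day 56.

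- Doses before the progression date: days 1 to 55, so 55 × 800 mg. Duration of the period that started before progression: 84 − 1 = 83 days. RDI = 55 / 83 = 66.3%.
- If cumulative dose instead means all of the sorafenib in periods that started before progression: RDI = 84 / 83 = 101.2%.

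The two descriptions of cumulative dose in the same section thus give 66.3% and 101.2% for one fully dosed patient.

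**Drug holidays.** Take 28 days on, 28 off and 28 on, all at full dose when on drug.

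- As written: 56 / (27 + 27) = 103.7%.
- With one day added per period: 56 / 56 = 100%.
- Over first to last dose: 56 / 84 = 66.7%.

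The added day therefore does not make holidays count; that needs a different denominator. Dose reductions do register under the present formula: 84 days at 800 mg, then 84 days at 400 mg, gives (84 × 800 + 84 × 400) / (83 + 83) / 800 = 75.9%, against 75.0% with inclusive counting.

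**The case against.** Four stronger readings are tempting, and the documents do not support them.

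1. A reader might infer that full-dose patients must exceed 100%. That depends on conventions the SAP leaves open. If the stop date is the first day off drug, if the first and last days are half-dosed, or if cumulative dose is itself computed as daily dose × (stop − start), the result is exactly 100%.

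2. A reader might infer that every dose change costs a day. It does so only if consecutive records do not share a date. With records on days 1–14, 14–28, 28–42 and 42–56, the sum is 13 + 14 + 14 + 14 = 55 days and RDI is 56 / 55 = 101.8%. Adding one day to each record would then give 59 days for 56 days of dosing, or 94.9%, so a bare correction could create a new error.

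3. A reader might infer that the formula overstates intensity throughout. The progression mismatch, where it applies, lowers intensity. It also disappears if the wording in the dose-intensity line governs, because that numerator and the duration then have the same scope.

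4. A reader might call the omission of gaps an arithmetic mistake. Summing administration periods is a recognisable on-drug measure, and SAP 6.5.1.2 separately reports reasons for dose delays and changes, duration and cumulative dose. Those items do not give the length of the gaps, however. If holidays were entered as 0 mg records and counted as periods, the 28/28/28 patient would have 56 / 81 = 69.1%, but the SAP does not say this.

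These objections limit the claim. They leave standing the departure from the SAP's own day-count convention, the undefined one-day case, the two cumulative-dose descriptions, and the absence of any intensity measure that reflects time off drug.

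**Conclusion.** The point holds as a minor one. The missing day matters for short or often interrupted courses and is small for long ones: 7.7 percentage points above 100% at 14 days and 0.6 at 24 weeks in a single period, provided that start and stop are both full dosing days. The zero denominator needs a patient whose only record before progression starts and stops on the same date. The progression mismatch can be larger and runs the other way (66.3% in the example), but only if the stand-alone cumulative dose is the numerator. Leaving out gaps is a choice of measure and has the largest effect on interpretation (103.7% against 66.7%), provided that holidays are not held as 0 mg periods.

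No efficacy test, significance level or sample size depends on these quantities. The per-protocol criteria in SAP 8.3.3 use receipt and timing of sorafenib, not its intensity. The effect is confined to descriptive exposure tables.

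**What to change.** Amend SAP 8.7.1.2 as follows.

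- State that the stop date is the last dosing day. Count distinct dosing days inclusively: stop − start + 1 for each period, with a date shared by consecutive records counted once. This also resolves the one-day record.
- Define cumulative dose once, and apply the same progression cut to cumulative dose and to duration.
- Label the present measure as on-drug dose intensity, and say how a holiday record is treated.
- Add, by arm, a dose intensity equal to cumulative dose before progression divided by (last dose date before progression − first dose date + 1), with the matching relative dose intensity.

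The cost is a few lines of SAP text and programming and one extra table row. No new data are needed beyond the dosing dates, dose changes and holidays that Protocol 9.2.18 already requires to be recorded.

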Although sorafenib is a SOC in the treatment of patients with HCC, it is associated with only a modest improvement in median survival as compared to best supportive care. Further, sorafenib treatment is associated with significant toxicity. The most common adverse reactions¹⁴ (≥ 20 percent) considered related to sorafenib were fatigue, weight loss, rash/ desquamation, hand-foot skin reaction, alopecia, diarrhea, anorexia, nausea and abdominal pain. Diarrhea was reported in 55 percent of sorafenib patients (grade 3 in 10 percent). Hand-foot syndrome (21 percent overall; grade 3 in 8 percent) and rash (19 percent overall; grade 3 in 1 percent) were the most common dermatologic adverse reactions to sorafenib. Sorafenib dose reductions and drug holidays are often required to manage these toxicities.

Subsequent subset analysis of the SHARP trial data⁶ indicated that the efficacy of sorafenib is reduced in an important subset of patients with advanced HCC. In patients with extrahepatic spread or macroscopic vascular invasion, the median survival was 8.9 months in patients treated with sorafenib as compared to 6.7 months in patients treated with placebo.

Salem et al⁷ recently published their long-term experience of TheraSphere in the treatment of patients with HCC. In this report, patients with HCC (n=291) were treated with TheraSphere as part of a single-center, prospective, longitudinal cohort study. Toxicities were recorded using the Common Terminology Criteria version 3.0. Response rate and time to progression (TTP) were determined using World Health Organization (WHO) and European Association for the Study of the Liver (EASL) guidelines. Survival by stage was assessed. Univariate/multivariate analyses were performed. A total of 526 treatments were

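### SAP 8.7.1.2 counts sorafenib days as stop minus start and has no rule for drug holidays, so relative dose intensity can exceed 100% at full dosing and can leave out interruptions (minor)

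*SAP*

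**What the plan says.** SAP 8.7.1.2 builds four sorafenib measures for the time before investigator-assessed progression:

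- Cumulative dose is the "sum of all administered doses prior to progression date per patient".
- Duration in weeks is the "sum of all sorafenib administration periods (stop date – start date) for sorafenib started prior to progression date /7".
- Dose intensity in mg/day is "Cumulative dose of sorafenib (mg) started prior to progression / (Duration of treatment (weeks) prior to progression *7".
- Relative dose intensity is the "dose intensity (mg/day) prior to progression divided by the one-day equivalent dose" of 2 × 400 = 800 mg/day, times 100.

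The next section, SAP 8.7.1.3, counts days inclusively for duration on study: "earlier of study exit date and death date – randomization date + 1". SAP 6.5.1.2 does the same for time to start of sorafenib. So do the formulas for TTP, TTUP, TTSP, TTDQoL, PFS, duration of response and duration of disease control in SAP 8.6.

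On interruptions, Protocol 5.3 says "Sorafenib dose reductions and drug holidays are often required to manage these toxicities". The protocol synopsis permits them, and Protocol 9.2.18 has dosing dates, dose changes and holidays recorded. SAP 6.5.1.4 names a sorafenib administration eCRF page. Neither document describes its rows, defines the stop date, or says how a holiday enters dose intensity.

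**The concern.** There are two separate problems in the denominator.

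1. Day count. If doses on both the first and the last day of a period are in the numerator, stop minus start is one day short for each separately dated period. Mg/day is then overstated, and a one-day exposure has a denominator of zero.
2. Holidays. A holiday is not an administration period. If it appears as a gap between periods, those days are in neither numerator nor denominator. The result is the average dose on dosing days, not the share of the reference dose delivered over time.

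A related mismatch is the cut-off. Cumulative dose is defined up to the progression date, whereas duration covers every period that started before progression and so can run past it. The dose-intensity line uses the second wording for the dose as well.

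What is at stake is the comparison of sorafenib delivery between arms. In a trial that adds TheraSphere before sorafenib, readers will use it to judge whether the added treatment displaced the standard one.

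**Working it through.** **Plan's own figure.** The reference dose is 2 × 400 = 800 mg/day, which reproduces.

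**Inputs.** The formulas are those of SAP 8.7.1.2. The schedules are illustrative assumptions, because the documents give none. One length used is 168 days, close to the 5.5-month median TTP on sorafenib cited in Protocol 5.3 (5.5 × 30.4375 = 167 days). Unless stated otherwise, the stop date is the last dosing day, doses on both end days are counted, and every dosing day is at 800 mg.

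**Step 1: day count.** With D dosing days in k separately dated periods, relative dose intensity = 100 × D/(D − k).

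| Schedule | SAP formula | With +1 per period |
|---|---|---|
| 168 days, one period | 168/167 = 100.6% | 100% |
| 28 days, one period | 28/27 = 103.7% | 100% |
| 168 days, four back-to-back 42-day records, no shared dates | 168/164 = 102.4% | 100% |
| 1 day | 1/0, undefined | 100% |

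**Step 2: holidays recorded as gaps.** Take a 168-day span with dosing on days 1–56 and 85–168, so 28 days off and 140 on.

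- SAP formula: 140/(55 + 83) = 140/138 = 101.4%.
- With +1 per period only: 140/140 = 100%.
- Over the span: 140/168 = 83.3%.

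The +1 alone does not bring the holiday back, so both changes are needed.

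**Step 3: sensitivity to what the documents leave open.**

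- Same holiday as a 0 mg row counted as a period: 140/(55 + 27 + 83) = 140/165 = 84.8%.
- Four records covering 168 days with shared change dates: 168/167 = 100.6%, so one day is lost in total, not one per record.
- Numerator built as daily dose × (stop − start): exactly 100% for a compliant patient.
- Half dose on the step 2 schedule: 70/138 = 50.7%, so a dose reduction is still visible.

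**Step 4: cut-off.** Take full dosing on days 1–126 with progression on day 113. If the numerator stops at progression (112 days of dose) and the denominator is the whole period (125 days), the result is 112/125 = 89.6%. With the dose-intensity line's own wording for both, it is 126/125 = 100.8%.

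**Step 5: pauses required in one arm.** Under the lung-exposure pathway in Protocol 9.2.15.1.3, a Treatment-group patient may start sorafenib, stop at least 7 days before TheraSphere and resume at least 2 weeks after. Assume 28 days on, 21 off and 63 on. The SAP formula gives 91/(27 + 62) = 91/89 = 102.2%; over the span it is 91/112 = 81.3%.

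**The case against.** The strongest reply is that the result depends on a record layout the documents do not show. With 0 mg rows, holidays are counted; with shared dates, only one day is lost; with a numerator on the same day count, a compliant patient shows exactly 100%. All of that stands. The conclusion is therefore conditional, and the SAP's silence on these conventions is part of the point.

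A reader might infer that every fully dosed patient must exceed 100%, that interrupted patients in general look fully dosed, and that the more interrupted arm is bound to be flattered. The documents do not support this. It requires particular conventions for the stop date, numerator and holidays, and it ignores that dose reductions still lower the figure. Overstatements well above a few percent need short or many separate periods; one long period gives under 1%. Nor is the inclusive count universal in the SAP: OS has no duration formula, and time from HCC diagnosis (SAP 6.3) is a plain difference.

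SAP 6.5.1.2 also plans cumulative dose, duration, time to start, and reasons for delays and changes. These limit how far reduced delivery could be hidden, though none gives the days lost.

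Finally, whether holidays belong in the denominator is partly a matter of definition. Intensity from first to last dose would count the pause in step 5 as under-dosing, in the Treatment group only. That objection is sound, and the fix has to allow for it.

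**Conclusion.** The point holds as a minor one. As written, the duration formula departs without explanation from the inclusive count used in the SAP's neighbouring formulas, and no rule returns interruption days to dose intensity.

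The day-count part is small for long single periods, larger for short or split ones, and undefined for one day. It assumes that the stop date is the last dosing day and that both end days are in the dose. The holiday part is the material one, about 18 percentage points in the 28-of-168-day example (101.4 − 83.3). It assumes that holidays are recorded as gaps and that dosing is full when on drug.

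The effect stops at descriptive exposure summaries. No efficacy test, sample-size figure or per-protocol exclusion in SAP 8.3.3 uses relative dose intensity.

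**What to change.** In SAP 8.7.1.2:

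- Define each period as stop date − start date + 1, and count a date shared by consecutive records once.
- Use the same day count and the same progression cut-off for cumulative dose and duration.
- Compute relative dose intensity from first to last sorafenib dose before progression, including interruption days whether recorded as gaps or as 0 mg rows.
- Keep the on-drug-days version as a separate, labelled summary.
- Report protocol-required interruptions around TheraSphere separately from toxicity holidays, so that the arms can be compared fairly.

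The cost is SAP wording and a short program change; version 5.0 of the SAP already revised this duration calculation once. Reported intensities will be somewhat lower. Nothing in treatment, data collection or efficacy analysis changes.
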